6.6 Duration of Follow-Up

Patients will be followed for 24 months from the time of enrollment *or* until death, whichever occurs first. Patients removed from study for unacceptable adverse event(s) will be followed until resolution or stabilization of the adverse event.

7. DOSING DELAYS/DOSE MODIFICATIONS

7.1 Recommended Dose Modifications of Lutetium Lu 177 Dotataate for Adverse Reactions

Adverse Reaction	Severity of Adverse Reaction	Dose Modification
Thrombocytopenia	Grade 2, 3, or 4	Withhold dose until complete or partial resolution (Grade 0 to 1). Resume Lutetium Lu 177 Dotataate at 100 mCi in patients with complete or partial resolution. If reduced dose does not result in Grade 2, 3 or 4 thrombocytopenia, administer Lutetium Lu 177 Dotataate at 200 mCi for next dose. Permanently discontinue Lutetium Lu 177 Dotataate for Grade 2 or higher thrombocytopenia requiring a treatment delay of 16 weeks or longer.
	Recurrent Grade 2, 3, or 4	Permanently discontinue Lutetium Lu 177 Dotataate.
Anemia and Neutropenia	Grade 3 or 4	Withhold dose until complete or partial resolution (Grade 0, 1, or 2). Resume Lutetium Lu 177 Dotataate at 100 mCi in patients with complete or partial resolution. If reduced dose does not result in Grade 3 or 4 anemia or neutropenia, administer Lutetium Lu 177 Dotataate at 200 mCi for next dose. Permanently discontinue Lutetium Lu 177 Dotataate for Grade 3 or higher anemia or neutropenia requiring a treatment delay of 16 weeks or longer.
	Recurrent Grade 3 or 4	Permanently discontinue Lutetium Lu 177 Dotataate.
Renal Toxicity	Defined as: 
• Creatinine clearance less than 40 mL/min; calculate using Cockcroft Gault with actual body weight, or• 40% increase in baseline serum creatinine, or• 40% decrease in baseline creatinine clearance; calculate using Cockcroft Gault with actual body weight.	Withhold dose until complete resolution. Resume Lutetium Lu 177 Dotataate at 100 mCi in patients with complete resolution. If reduced dose does not result in renal toxicity, administer Lutetium Lu 177 Dotataate at 200 mCi for next dose. Permanently discontinue Lutetium Lu 177 Dotataate for renal toxicity requiring a treatment delay of 16 weeks or longer.

Adverse Reaction	Severity of Adverse Reaction	Dose Modification
	Recurrent renal toxicity	Permanently discontinue Lutetium Lu 177 Dotatate.
Hepatotoxicity	Defined as: 
 • Bilirubinemia greater than 3 times the upper limit of normal (Grade 3 or 4), or • Hypoalbuminemia less than 30 g/L with a decreased prothrombin ratio less than 70%. • Grade 4 AST or ALT elevation 	Withhold dose until complete resolution. Resume Lutetium Lu 177 Dotatate at 100 mCi in patients with complete resolution. If reduced Lutetium Lu 177 Dotatate dose does not result in hepatotoxicity, administer Lutetium Lu 177 Dotatate at 200 mCi for next dose. Permanently discontinue Lutetium Lu 177 Dotatate for hepatotoxicity requiring a treatment delay of 16 weeks or longer.
	Recurrent hepatotoxicity	Permanently discontinue Lutetium Lu 177 Dotatate.
Other Non-Hematologic Toxicity	Grade 3 or 4	Withhold dose until complete or partial resolution (Grade 0 to 2). Resume Lutetium Lu 177 Dotatate at 100 mCi in patients with complete or partial resolution. If reduced dose does not result in Grade 3 or 4 toxicity, administer Lutetium Lu 177 Dotatate at 200 mCi for next dose. Permanently discontinue Lutetium Lu 177 Dotatate for Grade 3 or higher toxicity requiring treatment delay of 16 weeks or longer.
	Recurrent Grade 3 or 4	Permanently discontinue Lutetium Lu 177 Dotatate.

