7.2 Recommended Dose Modifications of Triapine

Dose modification should follow the triapine dose levels in the dose escalation table in Section 6.1.

Nausea/vomiting	Management/Next Dose for Triapine
≤ Grade 2	No change in dose. Treat with antiemetics.
Grade 3	Hold ^a until ≤ Grade 2. Resume at one dose level lower, if indicated. Treat with antiemetics.
Grade 4	Off protocol therapy ^c

^aPatients should hold triapine if N/V refractory to anti-emetic therapy.

^bIf appropriate antiemetic treatment does not resolve toxicity down to grade 2 or less within 72 hours.

^cOff protocol therapy and continue standard of care treatment per treating physician.

Diarrhea	Management/Next Dose for Triapine
≤ Grade 2	No change in dose. Treat with antidiarrheal therapy.
Grade 3	Treat with antidiarrheal therapy. Hold ^a until ≤ Grade 2. Resume at one dose level lower, if indicated ^b
Grade 4	Off protocol therapy ^b

^aPatients should hold triapine if diarrhea refractory to anti-diarrheal (Loperamide is recommended). Adjunct anti-diarrheal therapy is permitted and should be recorded when used.
^bOff protocol therapy and continue standard of care treatment per treating physician.

Neutropenia	Management/Next Dose for Triapine
≤ Grade 2	No change in dose
Grade 3	No change in dose
Grade 4	Off protocol therapy ^a

^aOff protocol therapy and continue standard of care treatment per treating physician.

Thrombocytopenia	Management/Next Dose for Triapine
≤ Grade 1	No change in dose
Grade 2	No change in dose
Grade 3	No change in dose
Grade 4	Off protocol therapy ^a

^aOff protocol therapy and continue standard of care treatment per treating physician.

Non-hematologic toxicity	Management/Next Dose for Triapine
≤ Grade 1	No change in dose
Grade 2	Hold ^{a, b} until ≤ Grade 1 (See NOTE below)
Grade 3	Hold ^c until < Grade 1 (See NOTE below)
Grade 4	Off protocol therapy ^b

^aPatients requiring a delay of >2 weeks should go off protocol therapy.
^b Grade 2 hypertension unrelated to study drugs in a patient with history of chronic hypertension does not warrant holding treatment.
^cOff protocol therapy and continue standard of care treatment per treating physician.
 NOTE: Decision to maintain dose or resume at dose reduction must be reviewed with study PI.

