12.1.1 Definitions

Evaluable for toxicity. All patients will be evaluable for toxicity from the time of their first treatment with study treatment.

Evaluable for objective response. Only those patients who have measurable disease present at baseline, have received at least three cycle of therapy, and have had their disease re-evaluated post-baseline will be considered evaluable for response. These patients will have their response classified according to the definitions stated below. Patients who exhibit objective disease progression prior to the end of Cycle 1 will also be considered evaluable.

Evaluable Non-Target Disease Response. Patients who have lesions present at baseline that are evaluable but do not meet the definitions of measurable disease, have received at least one cycle of therapy, and have had their disease re-evaluated will be considered evaluable for non-target disease. The response assessment is based on the presence, absence, or unequivocal progression of the lesions.

24-Month Progression-Free Survival: 24-month PFS is defined as the percentage of patients alive with no evidence of radiological progression per RECIST 1.1 at 24 months from the time of enrollment.

Overall survival: OS is defined as the time from date of enrollment to the date of death due to any cause.

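### After a first Grade 4 event, Section 7.1 resumes Lu-177 while Section 7.2 takes the patient off protocol therapy, and no rule says whether later Lu-177 doses count as cycles for response evaluability

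*Combined protocol and SAP*

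**What the plan says.** **Section 7.1 (Lu-177).** Grade 4 shares a row with lower grades: Grades 2 to 4 for thrombocytopenia, Grades 3 and 4 for anemia and neutropenia, and Grades 3 and 4 for other non-hematologic toxicity. On a first event Lu-177 is withheld, and after recovery the instruction is "Resume Lutetium Lu 177 Dotataate at 100 mCi in patients with complete or partial resolution". The full dose then follows: "If reduced dose does not result in Grade 3 or 4 anemia or neutropenia, administer Lutetium Lu 177 Dotataate at 200 mCi for next dose" for anemia and neutropenia, and "If reduced dose does not result in Grade 3 or 4 toxicity, administer Lutetium Lu 177 Dotatate at 200 mCi for next dose" for other non-hematologic events. Lu-177 stops for good on recurrence or after a long delay: "Permanently discontinue Lutetium Lu 177 Dotataate for Grade 3 or higher anemia or neutropenia requiring a treatment delay of 16 weeks or longer", with parallel wording in the other rows, such as "Permanently discontinue Lutetium Lu 177 Dotatate for Grade 3 or higher toxicity requiring treatment delay of 16 weeks or longer".

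**Section 7.2.** The heading is "Recommended Dose Modifications of Triapine" and each table column refers to triapine. The Grade 4 row reads off protocol therapy in all five tables: nausea/vomiting, diarrhea, neutropenia, thrombocytopenia and non-hematologic toxicity. The attached footnote adds that standard of care continues at the treating physician's discretion. In the non-hematologic table the Grade 4 cell is keyed to the hypertension footnote, apparently by mistake, but the cell text is the same.

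**Section 6.5.** Treatment may run for 4 cycles unless a listed criterion applies. The criteria include unacceptable adverse events and a treatment delay of more than 6 weeks.

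**Section 12.1.1.** To be evaluable for objective response a patient must have measurable disease at baseline, "have received at least three cycle of therapy", and a post-baseline assessment. The one exception to the three-cycle requirement is objective progression before the end of Cycle 1.

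**Section 9.5.** The overall response rate (ORR) gets an exact binomial 95% interval. The denominator is not stated.

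**The concern.** A site with a patient who recovers from a first Grade 4 event finds two instructions. The Lu-177 table says to continue after recovery. The triapine table ends protocol therapy, where it could have ended triapine alone. The protocol has agent-specific wording when it wants it: 7.1 speaks of discontinuing Lu-177, and the 7.2 footnotes on nausea/vomiting and diarrhea speak of holding triapine. The change of term at Grade 4 therefore reads naturally as an end to the whole regimen.

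Two things depend on the answer: how long such a patient stays on study treatment, and whether the patient enters the response-evaluable set. The patients concerned are selected by severe toxicity, so keeping or dropping them is not neutral for a response rate estimated on a few patients.

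**Working it through.** The point rests on a comparison of text. The plan gives no figure for it. Its one precision statement, in Section 9.1, concerns the DLT rate (17 patients, rate 0.25, exact 95% interval width 0.44). That figure reproduces (0.076 to 0.514, width 0.438) and is not at issue.

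**Step 1: scope of the term.** Section 4.4 speaks of a registered patient who never receives protocol therapy, 6.5 requires the reason and date of its discontinuation, and 11 times baseline tests from its start. All three mean study treatment as a whole. No passage narrows the term to triapine for 7.2.

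**Step 2: the same patient under each reading.** Planned treatment is four 8-week cycles. Take a first Grade 4 event that resolves and does not recur.

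| Event in | 7.1 followed for Lu-177: possible Lu-177 cycles | 7.2 read as whole regimen: protocol cycles | Meets three cycles? |
|---|---|---|---|
| Cycle 1 | up to 1 + 3 = 4 | 1 | possible under 7.1; no under 7.2 |
| Cycle 2 | up to 2 + 2 = 4 | 2 | possible under 7.1; no under 7.2 |
| After three cycles | up to 4 | 3 or 4 | yes under both; only duration can differ |

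If 7.2 is read as triapine only, the Cycle 1 patient can receive up to three further Lu-177 doses. Nothing says whether those doses are protocol therapy or cycles for 12.1.1. The narrower reading therefore leaves evaluability open too.

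**Step 3: delay limits.** Section 7.1 stops Lu-177 at a delay of 16 weeks or longer; 6.5 ends treatment at more than 6 weeks. For a delay above 6 and below 16 weeks, 7.1 permits resumption and 6.5 ends treatment. A footnote to the non-hematologic table in 7.2, attached to Grade 2, adds a third limit of 2 weeks.

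**Step 4: what reaches ORR.** A patient's evaluability changes only if all of these hold: the event comes before three cycles, it resolves, Lu-177 is actually resumed and carried to a third cycle, and the patient is not already evaluable through progression before the end of Cycle 1. The documents give neither a Grade 4 rate nor a response count, so the number of such patients is unknown.

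For scale only, assume 3 responders among the 14 expansion patients (both the 3 and the number removed are assumptions):

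- nobody removed: 3/14 = 21.4% (exact 95% interval 4.7% to 50.8%)
- one non-responder removed: 3/13 = 23.1% (5.0% to 53.8%)
- two non-responders removed: 3/12 = 25.0% (5.5% to 57.2%)
- one responder removed: 2/13 = 15.4% (1.9% to 45.4%)

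The last line is possible because Section 11 schedules scans every 8 or 12 weeks, so a response can be seen before three cycles are complete. The direction of the effect is therefore not fixed.

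**The case against.** **The two tables govern different drugs.** Section 7.2 is headed for triapine and its tables never mention Lu-177, which is a commercial agent given per label. One can apply 7.1 to Lu-177, stop triapine under 7.2, and treat further Lu-177 as the standard of care that the footnote allows. Section 6.1.1 ties triapine to Lu-177, but does not say that Lu-177 cannot continue alone. This reading is available, so a reader who inferred two opposing orders for one drug would go too far. What stands is that the term used is regimen-wide elsewhere, and that the triapine-only reading still leaves the status of later Lu-177 doses undefined.

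**The primary result.** Because safety is primary, a reader might infer that the conflict undermines it. The documents do not support that. DLTs are assessed at the end of Cycle 1 (6.2, 9.1), before any resumed dose. The safety analysis takes everyone who received study drugs (9.1), and all patients are evaluable for toxicity from first treatment (12.1.1). Section 9.1 defines no on-treatment window. The 30-day expedited-reporting window in 10.3.3 depends on the last administration of the investigational agent or intervention, but related serious events of Grade 3 or higher must be reported after it as well. Follow-up for PFS and OS runs 24 months from enrollment whatever happens to treatment (6.6).

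**Frequency.** It is tempting to compute the chance that at least one Grade 4 event occurs. That would need an assumed rate and would count events, such as those after three cycles, that cannot alter evaluability. It says little about this point.

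**Timing.** Accrual has closed. The note in 2.5.2.1 places closure before the biobanking decision, which 5.5.3.4 dates 12/13/2022. From then to the current version (17 May 2023) is 155 days. Less the 30 days allowed to start treatment (4.4), that is 125 days, or 17.9 weeks, so an undelayed patient would be in Cycle 3 at least. New dosing wording can reach few Cycle 1 or 2 events. The counting rule is still needed for the analysis.

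**Conclusion.** The point holds as an internal inconsistency with an analysis consequence. For a first Grade 4 neutropenia, thrombocytopenia or non-hematologic toxicity (nausea/vomiting and diarrhea included), 7.1 and 7.2 cannot both be followed if off protocol therapy has the meaning it has elsewhere. If it means triapine only, the protocol does not say what the remaining Lu-177 doses are. Section 6.5 adds a delay limit that disagrees with 7.1. Under the three-cycle rule, the response-evaluable status of a patient with a Grade 4 event before three cycles then depends on which section was followed.

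The reach is limited to treatment duration and the ORR denominator for those patients. ORR is secondary, and neither the size nor the direction of the effect can be derived from the documents. In the assumed 14-patient example, one or two removals move the estimate by 2 to 6 percentage points, well inside an interval of about 5% to 51%. The conclusion itself rests on the wording and not on those assumed counts.

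**What to change.** 1. Reconcile Sections 6.5, 7.1 and 7.2 so that the Grade 4 rows and the delay limits agree, and state whether off protocol therapy in 7.2 means triapine only or the whole regimen. Correct the footnote keys in the non-hematologic table in the same edit. Which clinical rule to adopt is for the investigators and the sponsor.
2. Add one rule to 12.1.1, cross-referenced in 9.5: whether Lu-177 cycles given without triapine count toward the three cycles, and which patients form the ORR denominator. Apply it to every patient, including those already treated, and fix it before response results are tabulated.

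The cost is a wording amendment and one analysis rule. No new patients or assessments are needed. Applying the rule to treated patients means checking, for each one, which cycles were given with and without triapine.

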7.2 Recommended Dose Modifications of Triapine

Dose modification should follow the triapine dose levels in the dose escalation table in Section 6.1.

Nausea/vomiting	Management/Next Dose for Triapine
≤ Grade 2	No change in dose. Treat with antiemetics.
Grade 3	Hold ^a until ≤ Grade 2. Resume at one dose level lower, if indicated. Treat with antiemetics.
Grade 4	Off protocol therapy ^c

^aPatients should hold triapine if N/V refractory to anti-emetic therapy.

^bIf appropriate antiemetic treatment does not resolve toxicity down to grade 2 or less within 72 hours.

^cOff protocol therapy and continue standard of care treatment per treating physician.

Diarrhea	Management/Next Dose for Triapine
≤ Grade 2	No change in dose. Treat with antidiarrheal therapy.
Grade 3	Treat with antidiarrheal therapy. Hold ^a until ≤ Grade 2. Resume at one dose level lower, if indicated ^b
Grade 4	Off protocol therapy ^b

^aPatients should hold triapine if diarrhea refractory to anti-diarrheal (Loperamide is recommended). Adjunct anti-diarrheal therapy is permitted and should be recorded when used.
^bOff protocol therapy and continue standard of care treatment per treating physician.

Neutropenia	Management/Next Dose for Triapine
≤ Grade 2	No change in dose
Grade 3	No change in dose
Grade 4	Off protocol therapy ^a

^aOff protocol therapy and continue standard of care treatment per treating physician.

Thrombocytopenia	Management/Next Dose for Triapine
≤ Grade 1	No change in dose
Grade 2	No change in dose
Grade 3	No change in dose
Grade 4	Off protocol therapy ^a

^aOff protocol therapy and continue standard of care treatment per treating physician.

Non-hematologic toxicity	Management/Next Dose for Triapine
≤ Grade 1	No change in dose
Grade 2	Hold ^{a, b} until ≤ Grade 1 (See NOTE below)
Grade 3	Hold ^c until < Grade 1 (See NOTE below)
Grade 4	Off protocol therapy ^b

^aPatients requiring a delay of >2 weeks should go off protocol therapy.
^b Grade 2 hypertension unrelated to study drugs in a patient with history of chronic hypertension does not warrant holding treatment.
^cOff protocol therapy and continue standard of care treatment per treating physician.
 NOTE: Decision to maintain dose or resume at dose reduction must be reviewed with study PI.

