3. PATIENT SELECTION

3.1 Eligibility Criteria

- 3.1.1 Metastatic, histologically confirmed well-differentiated neuroendocrine tumor with positive Dotatate scan (Gallium-68 or Copper-64) within 6 months. Lesions on Dotatate scan (Gallium 86 or Copper-64 Dotatate scan) will be considered positive if the SUV_{max} is >2 times SUV_{mean} of normal liver parenchyma.
- 3.1.2 Failure of at least one prior systemic cancer treatment, including somatostatin analogs.

3.1.3 Patients must have progressive disease based on RECIST Criteria, Version 1.1 evidenced with CT scans/MRI obtained within 24 months from enrollment.

3.1.4 Patients must have measurable disease per RECIST 1.1.

3.1.5 No prior exposure to peptide receptor radionuclide therapy.

3.1.6 Recovered from adverse events of previously administered therapeutic agents to Grade 1 or less toxicity according to CTCAE version 5.0.

3.1.7 Archival tissue no longer than 6 months old should be present, otherwise baseline research biopsy is needed for WES.

3.1.8 Age ≥ 18 years.

Because no dosing or adverse event data are currently available on the use of triapine in combination with Lutetium Lu 177 Dotataate in patients <18 years of age, children are excluded from this study, but will be eligible for future pediatric trials.

3.1.9 ECOG performance status 0,1, or 2 (Karnofsky $\geq 60\%$, see *Appendix A*).

3.1.10 Patients must have adequate organ and marrow function as defined below:

- leukocytes	$\geq 2,000/\text{mcL}$
- absolute neutrophil count	$\geq 1,500/\text{mcL}$
- platelets	$\geq 75,000/\text{mcL}$
- total bilirubin	$\leq 3 \times$ institutional upper limit of normal (ULN)
- AST(SGOT)/ALT(SGPT)	$\leq 3 \times$ institutional ULN
- glomerular filtration rate (GFR)	$\geq 50 \text{ mL/min}$ using Cockcroft-Gault method (see Appendix B)
- hemoglobin	$\geq 8.0 \text{ g/dL}$

3.1.11 Human immunodeficiency virus (HIV)-infected patients on effective anti-retroviral therapy with undetectable viral load within 6 months are eligible for this trial.

3.1.12 For patients with evidence of chronic hepatitis B virus (HBV) infection, the HBV viral load must be undetectable on suppressive therapy, if indicated.

3.1.13 Patients with a history of hepatitis C virus (HCV) infection must have been treated and cured. For patients with HCV infection who are currently on treatment, they are eligible if they have an undetectable HCV viral load.

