6.2 Definition of Dose-Limiting Toxicity

DLT will be defined by Grade 3 or greater hematological or non-hematological toxicity per CTCAE version 5.0 that is **possibly, probably or likely** related to study treatment. The following will not be considered DLTs unless determined to be clinically significant and related to study treatments by the treating physician:

- Grade 1-4 lymphopenia
- Grade 3 nausea, vomiting or diarrhea lasting <72 hours and controlled by optimal antiemetic/anti diarrheal therapy;

DLT will be assessed at the end of Cycle 1. Patients need to have at least one dose of Lutetium Lu 177 Dotatate and at least 80% of the dose cohort-specific triapine during Cycle 1 to be evaluable for adverse effects and DLT criteria for dose escalation/de-escalation decisions.

Management and dose modifications associated with the above adverse events are outlined in Section 7.

Dose escalation will proceed within each cohort according to the BOIN design described in Section 9.1. Dose-limiting toxicity (DLT) is defined above.

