6.5 Duration of Therapy

In the absence of treatment delays due to adverse event(s), treatment may continue for 4 cycles or until one of the following criteria applies:

- Disease progression (patient will however be monitored for OS)
- Intercurrent illness which would, in the judgment of the investigator, a) affect assessments of clinical status to a significant degree, b) require discontinuation of drug, or c) both a and b
- Unacceptable adverse event(s)
- Delay in treatment of more than 6 weeks.
- Patient decides to withdraw from the study
- General or specific changes in the patient's condition render the patient unacceptable for further treatment in the judgment of the investigator
- Clinical progression
- Patient non-compliance
- Pregnancy
 - All women of child-bearing potential should be instructed to contact the investigator immediately if they suspect they might be pregnant (e.g., missed or late menstrual period) at any time during study participation.
 - The investigator must immediately notify CTEP in the event of a confirmed pregnancy in a patient participating in the study.
- Termination of the study by sponsor

- The drug manufacturer can no longer provide the study agent

The reason(s) for protocol therapy discontinuation, the reason(s) for study removal, and the corresponding dates must be documented in the Case Report Form (CRF).

In April-May 2022 there was a global shortage of Lutetium 177 dotatate. Study enrollment and treatment was held per NCI CTEP's recommendation. The study was not affected as all patients had received cycle 1 of treatment had cleared DLT window. Delay in treatment due to global shortage will not trigger protocol deviation and treatment will resume when drug supply is restored. Patient will then get back on treatment schedule per protocol.

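### In the Section 7.2 non-hematologic table, the Grade 3 row tells sites both to hold triapine with a view to resuming and, through its footnote, to take the patient off protocol therapy

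*Combined protocol and SAP*

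**What the plan says.** The non-hematologic table in Section 7.2 has four rows, three lettered footnotes and a NOTE.

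- **Grade 2** (letters a and b): hold "until ≤ Grade 1 (See NOTE below".
- **Grade 3** (letter c): hold "until < Grade 1 (See NOTE below".
- **Grade 4** (letter b): off protocol therapy.
- **Footnote a** removes patients whose delay exceeds 2 weeks.
- **Footnote b** reads "Grade 2 hypertension unrelated to study drugs in a patient with history of chronic hypertension does not warrant holding treatment".
- **Footnote c** takes the patient off protocol therapy and on to standard care under the treating physician.
- **The NOTE**, cited by the Grade 2 and Grade 3 rows, reads "Decision to maintain dose or resume at dose reduction must be reviewed with study PI".

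Two other sections bear on this. Section 6.5 lists "Delay in treatment of more than 6 weeks" among the criteria that end treatment, without reference to grade. Criterion 3.1.6 admits patients who are "Recovered from adverse events of previously administered therapeutic agents to Grade 1 or less toxicity according to CTCAE version 5.0".

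**The concern.** The table decides who stops the investigational agent, and its Grade 3 row can be followed in two ways with opposite results. A site that reads the body of the row and the NOTE holds triapine, waits for recovery and takes the question of resuming to the study PI. A site that follows the footnote letter removes the patient. Nothing in Sections 6.5, 7.1 or 7.2 says which part governs.

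This affects triapine exposure, the rate of discontinuation for toxicity, and the set of patients who count for response. Section 12.1.1 requires at least three cycles for response evaluability, apart from patients who progress before the end of Cycle 1. A patient removed in Cycle 1 or 2 for toxicity would therefore normally fall out of the response denominator, while one held and resumed could stay in it.

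**Working it through.** The plan gives no figure to reproduce here. The check is to follow each letter to its footnote and compare it with the row.

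| Row | Body of the row | Letter | Where the letter leads | Consistent? |
|---|---|---|---|---|
| Grade 2 | Hold to Grade 1 or less, see NOTE | a, b | 2-week limit; hypertension exception | Yes |
| Grade 3 | Hold to below Grade 1, see NOTE | c | Leave protocol therapy | No: hold and resume against stop |
| Grade 4 | Off protocol therapy | b | Grade 2 hypertension exception | No: a Grade 2 exception on a Grade 4 row |

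**Readings of the Grade 3 row.**
1. The footnote governs: the patient goes off protocol therapy.
2. The body and NOTE govern: triapine is held and may resume after PI review. The 2-week limit is not lettered to this row, so the only general limit is the one in Section 6.5.

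**Delay limits as printed.** Grade 2 carries the limit of more than 2 weeks. Grade 3, on reading 2, carries only that of more than 6 weeks. The less severe event has the shorter limit, and the text does not say whether this is intended.

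**Recovery threshold.** As printed, below Grade 1 means Grade 0. A Grade 3 event that settles at Grade 1 would not permit resumption, whereas a Grade 2 event that settles at Grade 1 would. A patient who entered with a Grade 1 residual toxicity under 3.1.6 and then had Grade 3 of the same toxicity would have to improve on the entry state. This part rests on a single character and needs a check against the source file; the footnote conflict does not depend on it.

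**Other tables in Section 7.2.** In the diarrhea table, the Grade 3 instruction to resume one level lower also carries a letter leading to removal. In the nausea and vomiting table, footnote b is attached to no row.

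**Size for one patient.** Planned triapine days at once-daily dosing: 4 courses × 14 days = 56. Later courses at stake after a Cycle 1 event: 3 × 14 = 42. So up to 42 of 56 days, or 75%, depend on the reading. This assumes that the patient would otherwise have completed all four courses, and it leaves out any days remaining in the first course.

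**DLT evaluability.** Section 6.2 asks for "at least 80% of the dose cohort-specific triapine during Cycle 1". Of 14 doses, 80% is 11.2, so 12 are needed (12/14 = 85.7%; 11/14 = 78.6%). Both readings interrupt dosing at the event. They can differ here only if triapine restarts within the same course at the assigned dose after at most 2 missed doses.

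**The case against.** **The intent can be guessed.** The Grade 4 body and footnote c say the same thing, and in the nausea, neutropenia and thrombocytopenia tables the equivalent footnote sits on Grade 4 alone. Shifted lettering is a plausible explanation. That explains the fault but does not correct it, and the diarrhea table, which uses the removal footnote at both Grade 3 and Grade 4, weakens the inference.

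**PI review is required.** The NOTE stops a site from resuming on its own reading. It covers only maintaining or reducing the dose, so a site that follows footnote c could remove the patient without reaching that review.

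**The symbol may be an extraction fault.** A lost bar under the sign is possible. The correct sign survives in other rows of the same table, so the printed form stands until checked.

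**It comes late.** Section 2.5.2.1 places closure of accrual before the decision to bank the frozen blood, which Section 5.5.3.4 dates to 13 December 2022. Allowing 30 days to start (Section 4.4), then 168 days to Cycle 4 Day 1 and 13 more to Day 14, undelayed triapine would end about 12 July 2023, against a version dated 17 May 2023. A correction could reach few doses. The need to know which reading was applied remains.

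**Stronger readings that a reader might infer.**
- *Grade 3 holds have no time limit.* They do: Section 6.5 applies at any grade. What is missing is the 2-week limit.
- *Section 7.1 contradicts Section 7.2* because lutetium may resume after "Withhold dose until complete or partial resolution (Grade 0 to 2". The two sections govern different agents, and different thresholds are not in themselves a contradiction.
- *The recommended dose is undermined.* DLT is defined in Section 6.2 by grade and attribution, not by discontinuation, and the dose had already been selected (Sections 6.3.1 and 9.4.2).

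**Conclusion.** The conflict is real as printed. The Grade 3 row carries two incompatible instructions, the Grade 4 letter does not fit its row, and the 2-week limit reaches Grade 2 only. No other section resolves this. For a Cycle 1 event, up to 42 of 56 planned triapine days turn on the reading, on the assumption of otherwise complete once-daily treatment.

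The number of patients cannot be derived. The documents give no rate of Grade 3 non-hematologic events for this regimen, and nausea, vomiting, diarrhea and methemoglobinemia have rules of their own in Sections 7.2 and 7.2.1. A reader might infer a measurable shift in ORR or PFS; the documents support only that discontinuation, exposure and response evaluability could differ with the reading. The recovery threshold is a secondary point, conditional on the source check. The correction should be made, but the primary objective does not hang on it.

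**What to change.** 1. Reconcile the rows, footnote letters and NOTE of the non-hematologic table so that each grade carries one instruction. Check the diarrhea and nausea/vomiting letters at the same time.
2. State which grades the 2-week limit covers and how it fits with the 6-week limit in Section 6.5.
3. Check the Grade 3 recovery threshold against the source file. If it stands as printed, reconcile it with the Grade 2 row and with entry at Grade 1 under 3.1.6.
4. For patients already treated, record which reading was applied to each Grade 3 non-hematologic event, and report it with the discontinuations and the response-evaluable set.

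The investigators choose the clinical rule, and Section 7.1 need not use the same threshold. The cost is a correction to one table with a check of two neighbouring ones, a site memo, and a look back through the records of at most 29 patients.
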